9.1.2 Items to Be Investigated Concerning Adverse Events

If an AE develops during the clinical study, the items in Table 9-1 will be investigated and the results will be recorded. The subject should be questioned in a general way, without asking about the occurrence of any specific symptoms.

Table 9-1 Items to be Investigated for Adverse Event

Items reviewed	Content of review	
Content of AE	Name of AE, date of onset	
Action taken regarding the investigational product	None	No change in investigational product dosage was made.
	Discontinued Permanently	The investigational product was permanently stopped.
	Interrupted	The investigational product was temporarily stopped.
	Dose Reduced	The dosage of the investigational products was reduced.
Outcome	Classification of outcome, date of outcome assessment, date of resolution	
Classification of outcome	Recovered/Resolved	
 The subject fully recovered from the AE, with no residual effects observed.
	Recovered/Resolved with Sequelae	
 The residual effects of the AE are still present and observable. Identify sequelae/residual effects.
	Not Recovered/Not Resolved	
 The AE itself is still present and observable.
	Recovering/Resolving	
 The AE was almost fully resolved, and the subject recovered to near-baseline status.
	Unknown	
 No information and the outcome was unknown.
	Fatal	
Severity	Mild	Awareness of sign or symptom, but easily tolerated, ie, does not interfere with subject's usual function
	Moderate	Discomfort enough to cause interference with usual activity
	Severe	Incapacitating with inability to work or do usual activity, ie, interferes significantly with subject's usual function
Seriousness Definition of SAE	Serious (according to the following definition of SAEs) / Not serious 1. Results in death 2. Life-threatening 3. Requires inpatient hospitalization or prolongation of existing hospitalization 4. Results in persistent or significant disability/incapacity 5. A congenital anomaly/birth defect 6. An important medical event	

Table 9-1 Items to be Investigated for Adverse Event (cont.)

Items reviewed	Content of review	
Relationship to the investigational product	Classification of relationship (in accordance with the following classifications of relationship), reason for that assessment	
Classification of relationship	Related	
 The AE follows a reasonable temporal sequence from investigational product administration, and cannot be reasonably explained by the subject's clinical state or other factors (eg, disease under study, concurrent diseases, concomitant medications). The AE follows a reasonable temporal sequence from investigational product administration, and is a known reaction to the drug under study or its chemical group, or is predicted by known pharmacology.
	Not related	
 The AE does not follow a reasonable temporal sequence from investigational product administration, or can be reasonably explained by the subject's clinical state or other factors (eg, disease under study, concurrent diseases, concomitant medications).
Other action taken for event	None	No treatment was required.
	Medication required	Prescription and/or over-the-counter medication was required to treat the AE.
	Hospitalization or prolongation of hospitalization required	Hospitalization was required or prolonged due to the AE, whether or not medication was required.
	Other	

9.1.3 Definition of Adverse Drug Reaction

Those AEs for which the relationship to the investigational product is considered “Related” will be handled as adverse drug reactions (ADRs).

9.1.4 Actions to Be Taken When Adverse Events Occur

When an AE occurs, the investigator or sub-investigator will provide appropriate treatment, will report the AE to the sponsor if necessary, and to the extent possible will monitor progress until the subject recovers or the AE is resolved or relieved. If it appears unlikely from a medical perspective that the subject will recover, this will be explained to the subject, and monitoring of the subject as a part of the clinical trial will be concluded (although the treatment for the AE will be continued). In addition, clinical trial follow-up will be terminated and the clinical trial will be concluded if the investigator or sub-investigator decides further follow-up is unnecessary for the AE

because there is no relationship between the AE and the investigational product, or if the subject refuses further follow-up.

9.2 Actions to Be Taken When Serious Adverse Events Occur

If a serious adverse event (SAE) occurs after obtaining the subject's written ICF and up to Visit 11, the investigator or sub-investigator will provide appropriate treatment for the subject and will report the event via the eCRF to the sponsor within 24 hours after becoming aware of the event. The investigator will promptly entry a detailed information of the event to the sponsor in the eCRF. SAE reports will be prepared and submitted to the head of the study site or to the Institutional Review Board (IRB), using the form and procedures specified by the study site. Detailed information regarding the procedures for reporting SAEs is provided separately, in the standard operating procedures for SAEs.

In addition, the following types of events should be reported to the sponsor within 24 hours after becoming aware of the event in the designated form of the eCRF:

- Increase in ALT or AST $\geq 5 \times$ ULN
- ALT or AST rises to $\geq 3 \times$ ULN and persists for more than 2 weeks
- Concurrent increases in ALT or AST $\geq 3 \times$ ULN and T-Bil $\geq 2 \times$ ULN
- ALT or AST $\geq 3 \times$ ULN associated with a clinical presentation suggestive of liver injury (ie, including the appearance of fatigue, nausea, vomiting, jaundice, right upper quadrant pain or tenderness, fever, rash, and/or eosinophilia)
- AE related to suicide (if there are any "yes" responses to any of the questions in the C-SSRS)

The following types of events should be reported to the sponsor as promptly as possible after becoming aware of the event via the eCRF.

- Severe hepatobiliary adverse event
- Hepatobiliary Adverse event leading to Discontinuation
- Any transaminase elevation associated with a clinical presentation suggestive of Liver injury
- An elevation of ALT or AST $\geq 3 \times$ ULN (without clinical presentation suggestive of liver injury)

9.3 Exposure In Utero During Clinical Studies

Daiichi Sankyo must be notified of any subject who becomes pregnant while receiving or at the time of discontinuing the investigational product. All pregnancies must be

followed to conclusion to determine their outcome. This information is important for both drug safety and public health concerns. It is the responsibility of the investigator to report any pregnancy in a subject using the Exposure In Utero (EIU) Reporting form. The investigator will contact the study monitor to obtain the EIU Reporting Form upon learning of a pregnancy. If the outcome of the pregnancy meets the criteria for immediate classification as a SAE (ie, post-partum complications, spontaneous abortion, stillbirth, neonatal death, or congenital anomaly, including congenital anomaly in an aborted fetus), the investigator should follow the procedures for reporting SAEs.

9.4 Clinical Laboratory Evaluations

The study site staff will collect blood and urine specimens for routine laboratory tests at specified times. Specimens will be stored under conditions stipulated in the Sample Handling Manual until they are transported for measurement. Specimens will be transported and measured by a central laboratory. Table 9-2 summarizes the laboratory parameters to be assessed and the times of assessment.

Results of all laboratory tests will be reported from the central laboratory to the site.

A value or finding that represents a clinically significant abnormal change should be regarded as an AE, and should be described (diagnosed) appropriately in the CRF.

Table 9-2 Laboratory Parameters to be Assessed, and Time of Assessment

	Parameters	Time of assessment
Hematology	WBC, RBC, hemoglobin, hematocrit, platelet count, differential leukocyte (neutrophil, eosinophil, basophil, monocyte, lymphocyte) counts, reticulocyte count	
Blood chemistry	Total protein, albumin, A/G ratio, T-Bil, AST (GOT), ALT (GPT), ALP, γ -GT (γ -GTP), LDH, BUN, creatinine, uric acid, creatine kinase, total cholesterol, triglycerides, Na, K, Cl, Ca, Mg, inorganic phosphorus, bicarbonate, CRP	Visit 1, Visit 2, Visit 3, Visit 4, Visit 5, Visit 6, Visit 7, Visit 8, Visit 9, Visit 10, and Visit 11
Urinalysis	Standard urinalysis, including microscopic examination Specific gravity, pH, protein, glucose, ketones, urobilinogen, occult blood, RBC, WBC, bilirubin	
HbA1c	HbA1c	Visit 1, Visit 6, and Visit 10
Fasting blood glucose	Fasting blood glucose level	Visit 1, Visit 6, and Visit 10
Pregnancy	Qualitative test (urine)	Visit 1 and Visit 10

As described in Section 4.2.1, increases in aminotransferases have been observed in the DS-5565 development program to date. Special monitoring of such elevations during Phase 3 is described below. The Hepatic Adjudication Committee (HAC) charter includes a process by which selected cases will be adjudicated by a liver disease specialist (Section 11.10). In cases of liver laboratory abnormalities, it is important to ensure that the nature and the extent of liver injury is identified and study subjects are monitored until the liver laboratory assessments return to normal. Subjects who have any transaminase elevation associated with a clinical presentation suggestive of liver injury (ie, including the appearance of fatigue, nausea, vomiting, jaundice, right upper quadrant pain or tenderness, fever, rash, and/or eosinophilia) or an elevation of ALT or AST ≥ 3 x ULN (without clinical presentation suggestive of liver injury) at any visit should be monitored closely, according to the following:

- Repeat liver tests of at least all four of the usual serum measures (ALT, AST, alkaline phosphatase (ALP), and total bilirubin at least 2 times weekly (the first repeat should be within 48 to 72 hours of initial abnormality) until values have decreased to < 2 x ULN, then at least every 1 or 2 weeks until resolution or return to baseline. An additional serum separating tube of blood will be collected at time of event and until

values return to baseline. Samples will be stored for further analysis, as required.

[figure not shown]
- Review or obtain a detailed history of symptoms and prior or concurrent diseases.
- Review or obtain a history of the use of concomitant drugs, including nonprescription medications, herbal and dietary supplements, alcohol, recreational drugs, and special diets.
- Rule out alcoholic hepatitis; non-alcoholic steatohepatitis (NASH); hypoxic/ischemic hepatopathy; and biliary tract disease.
- Obtain a history of exposure to environmental chemical agents.
- Perform additional liver function tests (LFTs) (eg, serum lactate dehydrogenase (LDH), alkaline phosphatase (ALP), gamma-glutamyl transpeptidase (γ -GT [γ -GTP]), prothrombin time [PT]), evaluations for potential viral etiologies (including hepatitis A, B, C, E; cytomegalovirus [CMV]; Epstein-Barr virus [EBV]) and autoimmune etiologies (anti-nuclear antibody [ANA], anti-smooth muscle antibody [ASMA], anti-mitochondrial antibody [AMA]).

Combined elevations of aminotransferases and bilirubin meeting the criteria of a potential Hy's Law case [ALT or AST $\geq 3 \times$ ULN with simultaneous total bilirubin $\geq 2 \times$ ULN], either serious or non-serious and whether or not causally related, should always be reported to the sponsor within 24 hours (refer to Section 9.2), with the investigator's assessment of seriousness, causality, and a detailed narrative. (FDA's Guidance for Industry: Drug-Induced Liver Injury: Premarketing Clinical Evaluation; July 2009; <http://www.fda.gov/downloads/Drugs/Guidance/UCM174090.pdf>). These events should be reported as soon as possible following the procedures outlined in Section 9.2 for SAE reporting. The sponsor will be responsible for reporting the case(s) to the FDA.

Criteria for discontinuing subjects based on transaminase increases are provided in Section 4.2.1.

For subjects discontinued from the study due to any transaminase increase or hepatic event, the following should be performed:

- Gastroenterology or hepatology consultation
- Hepatobiliary ultrasound

a: ie, including the appearance of fatigue, nausea, vomiting, jaundice, right upper quadrant pain or tenderness, fever, rash, and/or eosinophilia

b: Evaluations for potential viral etiologies will include: Hep A Ab by IgM acute, HBsAg, HBeAg, anti-HBc, Hep C Ab, Hep C RNA by PCR, Hep E IgG Ab, Hep E IgM Ab, EBV IgG Ab, EBV IgM Ab, and CMV DNA by PCR

Abbreviations: ALP = alkaline phosphatase, ALT = alanine aminotransferase, AST = aspartate aminotransferase; CMV = cytomegalovirus, EBV = Epstein-Barr virus, γ-GT = gammaglutamyltransferase, LDH = lactate dehydrogenase, LFT = liver function test, PT = prothrombin time, ULN = upper limit of normal

9.5 Vital Signs

Vital signs will be recorded at all visits and will include supine pulse rate and supine and orthostatic blood pressure. For measurement of supine blood pressure, subjects should be in a supine or semirecumbent position for at least 5 minutes before the blood pressure measurement. Measurement of orthostatic blood pressure should follow measurement of supine blood pressure. Subjects should be asked to stand for 3 minutes before measurement of orthostatic blood pressure. Measurement of blood pressure should be conducted using a calibrated manometer or automatic inflatable cuff monitor; the blood pressure cuff should be kept in place between supine and orthostatic blood pressure measurements. Results will be recorded in the CRF.

9.6 Electrocardiograms

At the stipulated times (Visit 1 and Visit 10), 12-lead ECG will be performed. Results (Normal / Abnormal, not clinically significant / Abnormal, clinically significant) will be recorded in the CRF.

9.7 Physical Findings

9.7.1 Body Height and Weight

At Screening (Visit 1), body height will be measured. Body weight will be measured at each visit. Results will be recorded in the CRF.

9.7.2 Physical Examinations

At Screening Visit (Visit 1) and End of Treatment/Early Termination Visit (Visit 10), a complete physical examination, with the exception of pelvis, breast, and rectum in women and the genitourinary system and prostate in men, will be performed on each subject.

At Visit 2, Visit 3, Visit 4, Visit 5, Visit 6, Visit 7, Visit 8, Visit 9, and Visit 11, the examination should minimally include clinical evaluations of the head, neck, thyroid, eyes, ears, nose, throat, heart, lungs, lymph nodes, abdomen, skin, extremities, and musculoskeletal system.

Results will be recorded in the CRF.

9.7.3 Evaluation of Edema

At Visit 1 and Visit 10, evaluation of edema will be performed including physical

examination and/or pitting. Results (presence or absence of edema and expression site) will be recorded in the CRF.

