1.3 Risks and Benefits for Study Subjects

The results from nonclinical studies suggest that subjects treated with DS-5565 may experience improvement in DPNP, post-herpetic neuralgia (PHN), and fibromyalgia (FM). The clinical efficacy of DS-5565 has been evaluated in 2 Phase 2, multi-center, randomized, double-blind, placebo- and active-comparator controlled adaptive study in subjects with DPNP. In DS5565-A-U201 conducted in the US, DS-5565 15 mg QD, 10 mg BID, and 15 mg BID treatment groups demonstrated statistically significant mean reductions in ADPS from baseline to end-of-treatment compared to placebo. In DS5565-A-J202 conducted in Asian countries, DS-5565 5 mg BID, 10 mg BID, and 15 mg BID showed numerically mean reductions in ADPS, although the reduction was not statistically significant. These data provide proof-of-concept for DS-5565 as a treatment for DPNP and suggest that DS-5565 may have utility in other chronic pain conditions such as PHN and FM.

Anticipated risks of DS-5565 include the occurrence of adverse reactions related to CNS depression, such as dizziness and somnolence, as well as peripheral edema. Other notable TEAEs that have been observed in Phase 1 and Phase 2 studies include elevations of hepatic transaminases and suicide. For the approved $\alpha_2\delta$ ligands, in addition to dizziness, somnolence, and peripheral edema, certain adverse reactions requiring caution have also been reported, including but not limited to: weight gain, ophthalmologic disorders, suicidal behavior and ideation, angioedema, hypersensitivity, abrupt or rapid discontinuation, abuse potential, congestive heart failure, renal failure, and creatine kinase elevations.

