9.1 Adverse Events

9.1.1 Definition of Adverse Event

An AE is any unfavorable and unintended sign (including an abnormal laboratory value or abnormal vital sign), symptom, or disease that develops after the subject signs the Informed Consent Form (ICF) and up to 7 days after the last dose of study medication (Visit 11), regardless of relationship to the investigational product.

Any symptom that the investigator or sub-investigator considers associated with DPN will be evaluated as an efficacy variable and will not be regarded as an AE. However, if the symptom is considered potentially related to the investigational product, such symptom will be regarded as an AE. If any pre-existing symptom or disease is aggravated during the study period, the aggravation will be reported as an AE, and the date of confirming the aggravation will be considered the date of event onset.

Dizziness, somnolence, edema, and weight increase are currently defined as “significant AEs”. Any other significant AEs to be added will be specified in the statistical analysis plan (SAP).

All antiepileptic drugs carry a risk of increased suicidal behavior and ideation. Furthermore, increased hepatic transaminases have been observed in the DS-5565 development program. Therefore, the following “suicidal behavior and ideation” and “liver enzyme elevations/liver dysfunction” will be treated as adverse events of special interest.

- Increase in ALT or AST ≥ 5 x ULN
- ALT or AST rises to ≥ 3 x ULN and persists for more than 2 weeks
- Concurrent increases in ALT or AST ≥ 3 x ULN and T-Bil ≥ 2 x ULN
- ALT or AST ≥ 3 x ULN associated with a clinical presentation suggestive of liver injury (ie, including the appearance of fatigue, nausea, vomiting, jaundice, right upper quadrant pain or tenderness, fever, rash, and/or eosinophilia)
- Serious hepatobiliary adverse event
- Severe hepatobiliary adverse event

- Hepatobiliary Adverse event leading to Discontinuation
- Any transaminase elevation associated with a clinical presentation suggestive of Liver injury
- An elevation of ALT or AST $\geq 3 \times$ ULN (without clinical presentation suggestive of liver injury)
- AE related to suicide (if there are any “yes” responses to any of the questions in the C-SSRS)

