11.7.5 Physical Finding Analyses

Summary statistics will be calculated for measured values and changes from baseline in body weight at each scheduled visit. For the evaluation of edema, the results (presence

or absence) will be tabulated for each expression site.

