17. APPENDICES

17.1 Schedule of Events

Table 17-1 Study Visits

	Screening	Randomization	Treatment period							End of Treatment	Post-treatment follow-up ^{d)}	Early Termination
Visit	1	2	3	4	5	6	7	8	9	10	11	
Week	-1	0	1	2	4	6	8	10	12	14	15	
Day	≤ -7	1	8	15	29	43	57	71	85	99	Day 7 post-last-dose	
Visit window (days)	-7 to -14	—	6 to 10	13 to 17	26 to 32	40 to 46	54 to 60	68 to 74	82 to 88	96 to 102	Day 5 to 14 post-last-dose	
Informed consent	X ^{c)}											
Inclusion/exclusion criteria	X	X										
Demographic information	X											
Medical /surgical history	X											
Efficacy parameter(s) - see next table for details	X	X	X	X	X	X	X	X	X	X		X
Body height and weight	X	X ^{b)}	X ^{b)}	X ^{b)}	X ^{b)}	X ^{b)}	X ^{b)}	X ^{b)}	X ^{b)}	X ^{b)}	X ^{b)}	X ^{b)}
Physical examination	X	X	X	X	X	X	X	X	X	X	X	X
Evaluation of edema	X									X		X
Full neurological examination	X									X		X
Abbreviated neurological examination		X	X	X	X	X	X	X	X		X	
Ophthalmologic examination	X ^{c)}									X		X
Vital signs	X	X	X	X	X	X	X	X	X	X	X	X
12-lead ECG	X									X		X

CLINICAL STUDY PROTOCOL

AN ASIAN, PHASE 3, MULTICENTER, RANDOMIZED,
DOUBLE-BLIND, PLACEBO-CONTROLLED 14-WEEK STUDY OF
DS-5565 IN PATIENTS WITH DIABETIC PERIPHERAL NEUROPATHIC
PAIN FOLLOWED BY A 52-WEEK OPEN-LABEL EXTENSION

-For Open-Label Extension study-

DS5565-A-J303

VERSION 6.0, 18 Apr 2016

DAIICHI SANKYO

CONFIDENTIALITY STATEMENT

Information contained in this document is proprietary to Daiichi Sankyo. The information is provided to you in confidence which is requested under an agreed upon and signed Confidentiality and Disclosure Agreement. Do not give this document or any copy of it or reveal any proprietary information contained in it to any third party (other than those in your organization who are assisting you in this work and are bound by the Confidentiality and Disclosure Agreement) without the prior written permission of an authorized representative of Daiichi Sankyo.

IMPORTANT STUDY ADMINISTRATIVE INFORMATION

Sponsor	Daiichi Sankyo Co., Ltd. [name] TEL: see Section 15.10 FAX: see Section 15.10
Contract Research Organization (Japan):	CMIC Co., Ltd. [name] PPD [REDACTED] PPD [REDACTED]
Contract Research Organization (Korea):	Quintiles Transnational Korea Co., Ltd. [name] PPD [REDACTED] PPD [REDACTED]

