9.7.3 Evaluation of Edema

Evaluation of edema will be performed, including physical examination and/or pitting, at each visit excepting Visit 25. Results (presence or absence of edema and expression site) will be recorded in the CRF.

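### The structured edema evaluation has a single post-dose look per completer in the placebo-controlled study, so it gives end-of-treatment prevalence rather than incidence and cannot be set beside the extension's visit-by-visit record

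*Combined protocol and SAP*

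**What the plan says.** Section 1.3 lists the anticipated reactions as "dizziness and somnolence, as well as peripheral edema". Section 9.1.1 makes edema a predefined significant AE: "Dizziness, somnolence, edema, and weight increase are currently defined as" significant AEs.

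In the double-blind study, section 9.7.3 schedules the structured evaluation as follows: "At Visit 1 and Visit 10, evaluation of edema will be performed including physical" examination or pitting, with presence and site entered in the CRF. The row "Evaluation of edema" in Table 17-1 is marked at screening, end of treatment and early termination only. Sections 6.2, 6.3 and 6.5 do not list it.

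In the open-label extension, section 9.7.3 schedules the same evaluation "at each visit excepting Visit 25".

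The other routes by which edema can be recorded in the double-blind study are:

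- **Physical examination (9.7.2).** At Visits 2 to 9 and 11, "the examination should minimally include clinical evaluations of the head, neck, thyroid, eyes, ears, nose, throat, heart, lungs, lymph nodes, abdomen, skin, extremities" and the musculoskeletal system, with results entered in the CRF.
- **AE reporting (9.1.2).** AEs are evaluated at every visit, but the subject is questioned in general terms, "without asking about the occurrence of any specific symptoms".
- **Body weight (9.7.1).** Measured at every visit.

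For analysis, section 11.7.5 says: "For the evaluation of edema, the results (presence" or absence) are tabulated for each site. It names no visit, no shift from baseline and no definition of new edema. Section 11.7.1 tabulates TEAEs by treatment, with significant TEAEs as a category and a breakdown by preferred term.

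**The concern.** The only part of the programme described here that can attribute edema to the drug is the randomised comparison with placebo. That is where the structured record is sparse. It is dense in the extension, which has no control arm.

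A subject whose edema appears during or after titration and has gone by Week 14 is edema-free in the structured data. The structured table can therefore compare arms on how many subjects have edema at the end. It cannot compare them on how many developed it or when. An end-of-treatment prevalence from the double-blind part and a visit-by-visit record from the extension are also different quantities, and should not be read against each other.

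**Working it through.** **Visit counts**

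| | Double-blind | Extension |
|---|---|---|
| Scheduled visits | Visits 1 to 11: 11 | Visits 10 to 25: 16 |
| With structured edema evaluation | Visits 1 and 10: 2 | Visits 10 to 24: 15 |
| Post-dose, on-treatment visits | Visits 3 to 10: 8 | Visits 11 to 24: 14 |
| Of these, with the evaluation | 1 of 8 | 14 of 14 |

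Subjects who withdraw also have one post-dose look, at early termination, as far as they cooperate (4.2.3).

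**What one look can find.** The plan gives no edema rate, onset time or duration, so there is no figure of its own to reproduce. What follows is an illustration under stated assumptions: exponential duration with mean m weeks, visits at Weeks 1, 2, 4, 6, 8, 10, 12 and 14 (Table 17-1), and early-termination looks ignored.

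*Onset uniform over 14 weeks*

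- Present at Visit 10: P = (m/14)(1 − exp(−14/m)).
- Present at one or more of Visits 3 to 10: an episode is found if it lasts to the next visit. The gaps between visits are two of 1 week and six of 2 weeks, so P = [2m(1 − exp(−1/m)) + 6m(1 − exp(−2/m))]/14.

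For m = 4, the first is (4/14)(1 − 0.030) = 0.277. The second is [8(0.2212) + 24(0.3935)]/14 = (1.770 + 9.443)/14 = 0.801.

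*Onset uniform over the first 4 weeks*

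- Visit 10: P = (m/4)(exp(−10/m) − exp(−14/m)).
- Visits 3 to 10: P = [2m(1 − exp(−1/m)) + m(1 − exp(−2/m))]/4.

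| Assumed mean duration (weeks) | 2 | 4 | 8 | 14 | 26 |
|---|---|---|---|---|---|
| Onset over 14 weeks: Visit 10 only | 14% | 28% | 47% | 63% | 77% |
| Onset over 14 weeks: Visits 3 to 10 | 65% | 80% | 89% | 94% | 97% |
| Onset in first 4 weeks: Visit 10 only | 0.3% | 5% | 23% | 43% | 63% |
| Onset in first 4 weeks: Visits 3 to 10 | 71% | 84% | 91% | 95% | 97% |

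The single look finds less than half of episodes only if mean duration is below about 8.8 weeks (uniform onset) or about 17 weeks (early onset). Visit-by-visit recording finds more in every column, and the gain shrinks as duration lengthens.

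**The case against.** The strongest reply is that edema is already captured throughout the controlled study, and much of that reply stands.

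- **AE tables.** A reader might infer that the table in 11.7.5 is the only placebo-controlled edema table. It is not. Section 11.7.1 gives significant TEAEs and preferred terms by arm, and 11.7 puts all safety analyses on a by-treatment basis.
- **Examiner-observed edema.** The AE definition in 9.1.1 covers signs as well as complaints, so edema seen at an examination is reportable. Table 9-1 records its onset, outcome and resolution dates. The rule on general questioning limits what subjects are asked, not what examiners may report.
- **Examination findings and weight.** Skin and extremity findings at the intermediate visits do go into the CRF. Weight is summarised by visit as change from baseline, and section 3.2 of the extension gives evaluating edema as the reason for measuring it.
- **Analysis detail.** Section 11.2 defers detail to a separate SAP, which may specify the layout of the edema table.

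These points narrow the concern without closing it. Reporting an observed sign as an AE depends on each site's judgement, whereas the edema field requires a yes or no. No analysis of the intermediate extremity findings is stated in 11.7.5. Weight increase is itself a separate significant AE, so weight cannot isolate edema. A later SAP can define a table, but it cannot supply presence-or-absence records that were not scheduled.

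**Conclusion.** The point holds as a modest weakness in the design of one safety measurement. In the double-blind study 7 of 8 on-treatment visits have no structured edema record, against none of 14 in the extension. The structured data give point prevalence at end of treatment (or at early termination), and edema that resolves earlier depends on AE reporting to reach a controlled table.

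A reader might go further and infer that most on-treatment edema is missed. The documents do not support that. They give no duration, the result crosses one half within a plausible range of assumptions, early-termination looks are left out of the illustration, and AE reporting runs in parallel. The percentages show how far the answer depends on duration; they do not estimate a loss.

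Nor do the documents support saying that reversibility off drug goes unobserved. Visits 11 and 25 include a physical examination, weight and AE evaluation, and AEs are followed towards resolution where possible (9.1.4). Only the structured field is absent there.

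The primary efficacy analysis, the sample size and the study stopping rules are unaffected.

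**What to change.** 1. In sections 9.7.3, 6.2 and 6.3 and in Table 17-1 of the double-blind protocol, add the existing edema field (presence and site) to the physical examination already scheduled at Visits 2 to 9. Visit 2 then also supplies a baseline close to the first dose.
2. In 11.7.5, tabulate by arm the number and percentage of subjects with new or worsened edema relative to baseline at any on-treatment visit, and present it alongside the TEAE tables. The field has no grade, so define worsening in advance, for example as edema at a site not affected at baseline.
3. Optionally, record the field at Visit 11 and at extension Visit 25, where a physical examination already takes place. Report Visit 11 descriptively only: follow-up is not required for subjects who enter the extension, so those seen there are a selected group.

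The cost is one more CRF field per visit, with no new visit or procedure. The downside is that some additional mild edema will be recorded in all arms, placebo included.
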